1.2.13 Date of First Enrollment

June 9, 2022.

1.2.14 Sample Size

Planned:

- Group 1 (eTEP): 30 participants
- Group 2 (Rives-Stoppa, control): 30 participants

Actual:

- Group 1 (eTEP): 30 participants
- Group 2 (Rives-Stoppa, control): 30 participants

1.2.15 Recruitment Status

Completed.

1.2.16 Primary Outcomes

- Outcome name: Length of hospital stay

Method of measurement: Time (days) spent within the hospital Timepoint: Start at day of operation (day zero) until day of discharge

Outcome name: Postoperative pain management

Method of measurement: Modality (type, generic name), duration (days), dosage (grams or

milligrams) and frequency (times per day) of analgesics administration

Timepoint: During hospital stay

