1.2.12 Study Type

Single-center, observational study.

Non-randomized allocation:

- Group 1 (eTEP): First 30 patients who meet the inclusion criteria and do not exhibit any of the exclusion criteria will be investigated. The option for endoscopic eTEP repair, if feasible, is given preoperatively as a standard for the treatment of symptomatic midline abdominal wall hernias with concomitant rectus abdominis diastasis as an alternative to open Rives-Stoppa mesh repair. The modality of operative treatment is made in cooperation with the patient.
- Group 2 (Rives-Stoppa, control): Thirty patients will be selected out of all patients who underwent an open Rives-Stoppa (midline repair with sublay mesh) in our center and who do not meet any of the exclusion criteria. Patient selection will consist of matching to patients in group 1 according to gender and age (e.g. a male patient in group 1 will be matched to a male patient (group 2) out of our records

who underwent an open Rives-Stoppa repair and whose age most closely resembles the age of the matched patient in group 1).

Masking: None.

Assignment: Two-group, parallel.

Purpose: Comparing two routinely used interventions for the treatment of midline abdominal wall hernias with rectus abdominis diastasis.

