1.2.20 Summary of Results

Date of posting of results summaries: December 26, 2022 (within study protocol).

Date of the first journal publication of results: Not yet achieved.

[figure not shown]
URL: Not (yet) applicable.

Baseline characteristics:

- Group 1 (eTEP): EHS Registry: BEGZ, BEHA, BEHB, BEJR, BEJS, BEJT, BEJW, BEJX, BEJZ, BEKA, BEKB, BEKC, BEKG, BEKH, BEKI, BEKJ, BEKK, BEKK, BEKM, BELE, BELF, BELG, BELH, BELI, BELJ, BELK, BELL, BEOD, BETJ, BETK.
- Group 2 (Open RS): EHS Registry: BELN, BELO, BELQ, BELR, BELS, BELT, BELU, BELV, BELV, BELY, BEOF, BEOH, BEOO, BEPV, BEPX, BEPY, BEPZ, BEQA, BEQF, BEQG, BEQJ, BEQK, BEQQ, BEQR, BEQS, BEQT, BEQV, BEQX, BETN, BETO.

Participant flow (see also participant flowchart on next page):

Date	Group 1	Group 2
June 9, 2022	23 participants	23 participants
June 13, 2022	24 participants	24 participants
June 17, 2022	25 participants	25 participants
June 20, 2022	26 participants	26 participants
June 21, 2022	27 participants	27 participants
July 11, 2022	28 participants	28 participants
August 30, 2022	30 participants	30 participants

Adverse events:

- Three conversions were needed in group 1 (eTEP) because no adequate visualization could be achieved (1 participant) or because the diastasis was deemed to large to be appropriately closed endoscopically (2 participants)
- Observed complicationa according to the Clavien-Dindo (CD) classification [3]:
 During hospital stay in the eTEP group: 1x CD I, 12x CD II.

 During hospital stay in the Open RS group: 4x CD I, 10x CD II, 4x CD IIIb.

 After discharge until 30 days in the eTEP group: 5x CD I, 1x CD II, 2x CD IIIa, 1x CD IIIb.

 After discharge until 30 days in the Open RS group: 5x CD I, 1x CD II, 5x CD IIIa, 4x CD IIIb.

Outcome measures: See brief summary.

URL protocol files: Not applicable.

Brief summary:

- Median length of hospital stay was longer in the open RS group.
- Median duration of patient-controlled analgesia was longer in the open RS group.
- Switch to only oral analgesics took longer in the open RS group.
- No significant difference in 'comparable parameter'* for postoperatively administered analgesics irrespective of PCA between both groups.
- No significant difference between the presence of prescription opioids at discharge.
- Median duration of surgery (skin-to-skin time) was significantly shorter in the open RS group.
- Need for drainage (postoperative drain inserted during primary surgery) was significantly greater in the open RS group.

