- No early recurrences were found in both groups (postoperative consultation at approximately one month after surgery).
- Bulging of the abdominal midline was seen in 11 participants in the eTEP group and was not seen in the open RS group, this difference was statistically significant.

*Comparable parameter: Types of analgesics were divided into three categories. Category 1 contained only paracetamol, category 2 contained all non-steroidal anti-inflammatory drugs, and category 3 consisted of all opioids. A combination of active substances (in one analgesic) of which at least one was an opioid was seen as category 3. For each participant the absolute amount of analgesics in each category was calculated between postoperative day one and the day before discharge, this amount was divided by the amount of days between postoperative day one and the day before discharge.

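### The in-hospital analgesic outcome takes no account of analgesics used before surgery, so continued home medication can blur, mask or create a group difference

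*Protocol*

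**What the plan says.** Protocol section 1.2.16 lists two primary outcomes. The second is introduced as "Outcome name: Postoperative pain management". It is measured by type, duration, dosage "milligrams) and frequency (times per day) of analgesics administration", with "Timepoint: During hospital stay". Nothing limits it to drugs started because of the operation.

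Section 1.2.20 gives the working form, called there the comparable parameter. Paracetamol is the first category; for the rest, "category 2 contained all non-steroidal anti-inflammatory drugs, and category 3 consisted of all opioids". The calculation is then: "For each participant the absolute amount of analgesics in each category was calculated between postoperative day one and the day before discharge", divided by the number of days in that window. No preoperative regimen is subtracted or flagged. The same section reports no significant difference in this parameter, and it has one result line on discharge: "No significant difference between the presence of prescription opioids at discharge".

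On who enters the comparison, section 1.2.11 excludes by certain intraoperative procedures and, in the eTEP group, by absence of hernia or diastasis. Neither list mentions prior analgesic use. In section 1.2.12 allocation is non-randomised ("The modality of operative treatment is made in cooperation with the patient"), and each control is chosen by gender and nearest age.

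**The concern.** The outcome is meant to show how much pain treatment patients need after each technique. A patient who took an analgesic before admission and continues it in hospital adds that drug to the daily amount whichever operation was done. If it is an opioid that is prescribed again on leaving, the patient may also count as having an opioid at discharge.

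If prior use is similar in the two groups, this mainly adds variability and makes a real difference harder to see. If prior use is unequal, it moves the contrast in one direction or the other. The design has nothing that makes equality likely: the operation was not randomised, and prior use is neither an exclusion nor a matching variable.

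What is at stake is chiefly the reading of the two null results in section 1.2.20. Neither can be taken to mean that postoperative analgesic need was the same without knowing who was already taking analgesics.

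**Working it through.** **No figure to reproduce.** The protocol gives 30 per group (1.2.14) without alpha, power, effect size or standard deviation, and it gives no count of prior users. The arithmetic below shows scale on assumed inputs; it does not estimate what happened in this study.

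**1. The text side by side.** Section 1.2.16 counts analgesics administered. Section 1.2.20 counts the absolute amount by category, from postoperative day one to the day before discharge. Day zero and the day of discharge fall outside that window, but a regular home drug is counted on every day inside it. Sections 1.2.11 and 1.2.12 neither remove nor balance prior users. Section 3.1.9 says that data come from the electronic medical records and does not mention preoperative medication.

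**2. Shift in mean daily amount.** If one group has k more prior users, each on h home doses a day, its mean moves by k × h / 30.
- k = 3, h = 2 to 4 (assumed): 6/30 = 0.20 to 12/30 = 0.40 doses a day.
- k = 5, h = 2 to 4 (assumed): 10/30 = 0.33 to 20/30 = 0.67 doses a day.

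**3. What a fixed shift does to a test.** Assume a two-sided 5% test and a standard deviation (SD) of 1.0 to 2.0 doses a day. The standard error is SD × √(2/30) = 0.258 × SD, and the rejection rate is Φ(shift/SE − 1.96) + Φ(−shift/SE − 1.96).
- Shift 0.3: 21% at SD 1.0, 9% at SD 2.0.
- Shift 0.5: 49% at SD 1.0, 16% at SD 2.0.

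These rates apply with no effect of technique.

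**4. Masking.** With 30 per group, 80% power needs a standardised difference of (1.960 + 0.842) × 0.258 = 0.72. If a true difference of that size were offset by 0.3 SD from unequal prior use, power would be about Φ((0.72 − 0.30)/0.258 − 1.96) = Φ(−0.32), or 37%.

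**5. How easily groups of 30 differ.** Let X and Y be independent binomial counts of prior users, with n = 30 and the same true prevalence in both groups. P(|X − Y| ≥ 3) is 13%, 27%, 36% and 42% at assumed prevalences of 5%, 10%, 15% and 20%. Chance imbalance of this kind is part of ordinary sampling error: it widens the SD and does not by itself bias the test. It does show that similar counts cannot be taken for granted, before any selection through the choice of operation.

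**6. Discharge opioids.** Each prior user who leaves with an opioid moves that group's proportion by 1/30 = 3.3 points. An assumed imbalance of 2 to 4 such patients moves the contrast by 2/30 = 6.7 to 4/30 = 13.3 points. This measure is a result line in section 1.2.20, not a registered primary outcome.

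**The case against.** **The protocol is silent; it does not say that home drugs are included.** A reader might infer that the plan deliberately counts them. It does not say so, and the outcome's name points towards treatment of surgical pain. A rule on home drugs, or adjustment for prior use, could stand in a statistical analysis plan that is not shown. Baseline data appear only as registry codes, so prior use may have been recorded. All this stands and limits the claim. What remains is that the counting rule itself is written in the protocol and sets no limit.

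**A reader might infer that long-term analgesic use is being scored as an effect of the operation.** The document does not support that. Bias needs unequal prior use, and nothing shows it or links it to the choice of operation. No group difference was claimed on either exposed measure. The differences that were reported, duration of patient-controlled analgesia and time to oral-only analgesics, are not prolonged merely because a patient takes an oral home drug. Even 4 of 30 against 0 of 30 with an opioid at discharge gives a two-sided Fisher p of 2 × C(30,4)/C(60,4) = 2 × 27,405/487,635 = 0.11. Masking remains possible, however, and matters most for null results.

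**This is confounding rather than a faulty outcome.** That is largely right as to bias: balanced prior use would leave mainly noise. Total consumption is a defensible outcome and need not be replaced.

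**Subtracting home use could introduce its own bias.** Controls come from past records. If home medication was recorded less completely for older controls, the missed use would be counted as new analgesia after open repair, in favour of eTEP. This stands, and it is why the fix keeps the registered outcome.

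**Conclusion.** The point holds in a limited form. As defined, the analgesic outcome takes no account of preoperative use, and neither the exclusions nor the matching controls for it. Continued home medication can add noise, and can hide or produce a difference if prior use is unequal. The amount per day and opioid prescription at discharge are the exposed measures; duration of patient-controlled analgesia is less so.

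Direction and size cannot be determined from the document. The illustrative shifts of 0.2 to 0.67 doses a day, and of 6.7 to 13.3 points at discharge, rest wholly on assumed numbers of prior users, home doses and standard deviations. If there were no prior users, one sentence saying so would settle the matter. Until then, the two null results should not be read as equal postoperative analgesic need.

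**What to change.** - Keep total consumption as the registered outcome.
- Extract preoperative analgesic and opioid use from the electronic records already under review, and report the number of prior users in each group.
- Add a supplementary analysis of the amount per day that adjusts for prior use or leaves out preoperative opioid users, labelled as added after the registered outcome.
- Report new opioid prescriptions at discharge beside any opioid prescription.
- State as a limitation that home-medication lists may be less complete for older control records.

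The cost is a little more record review for 60 patients and a re-run of the analgesic comparisons. Section 1.2.20 states that journal publication had not yet been achieved, so at this protocol version the additions could still enter the report. No change to patient care is involved.

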1.2.17 Secondary Outcomes

- Outcome name: Intraoperative complications

Method of measurement: Adverse event occurrence

Timepoint: During surgery

- Outcome name: Postoperative complications

Method of measurement: Adverse event occurrence by readmission

Timepoint: After discharge until 30 days postoperative

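### The post-discharge complication outcome is defined by readmission but reported by Clavien-Dindo grade without readmission status, so the defined outcome cannot be recovered

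*Protocol*

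**What the plan says.** Section 1.2.17 of the protocol lists postoperative complications as a secondary outcome. The detection rule is "Method of measurement: Adverse event occurrence by readmission" and the window is "Timepoint: After discharge until 30 days postoperative".

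Section 1.2.20 reports complications "according to the Clavien-Dindo (CD) classification". For the same window, its line for the endoscopic group is "After discharge until 30 days in the eTEP group: 5x CD I, 1x CD II, 2x CD IIIa, 1x CD IIIb". The matching line for the control group, set out in the same way, is "After discharge until 30 days in the Open RS group: 5x CD I, 1x CD II, 5x CD IIIa, 4x CD IIIb".

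No readmission count or readmission flag accompanies these figures. The protocol cites the classification but does not define its grades or link them to admission.

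Four other places bear on the point. Section 2.1.2 names complications, not readmissions, as what is to be compared. Section 3.1.9 gives review of the electronic medical records as the data source, with no restriction to readmissions. Sections 1.2.12 and 3.1.8 state that there was no masking. Sections 3.1.8, 3.1.9 and 4.1.8 show that the same contributor matched the controls, collected the data and analysed them.

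**The concern.** The rule and the result are expressed in different terms. Readmission describes how an event came to notice; a CD grade describes its severity. A table by grade does not show how many events satisfy a readmission rule.

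This matters in either of two cases. If the rule was followed, the outcome is a readmission outcome under the name of complications, and anything managed at an outpatient or emergency visit without admission is left out. If it was not followed, some wider rule decided which events entered the table. The protocol states no such rule, and the list of additions at its head mentions no change to 1.2.17. An unstated rule leaves the inclusion of borderline events to a record reader who knows the treatment group.

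**Working it through.** **Inputs.** Actual group sizes (1.2.14): "Group 1 (eTEP): 30 participants" and "Group 2 (Rives-Stoppa, control): 30 participants". Event counts by grade after discharge to day 30 come from 1.2.20. The protocol gives no total, test or power figure for this outcome, so there is no stated result to reproduce.

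**Step 1, totals.**
- eTEP: 5 + 1 + 2 + 1 = 9, of which CD I-II: 5 + 1 = 6 (67%) and CD III: 2 + 1 = 3.
- Open RS: 5 + 1 + 5 + 4 = 15, of which CD I-II: 5 + 1 = 6 (40%) and CD III: 5 + 4 = 9.

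**Step 2, what the readmission rule would count.** Readmission status is not given, so only bounds under assumptions are possible.
- If every listed event was a readmission, 0 of 9 and 0 of 15 drop out.
- If no CD I-II event was a readmission, at least 6 drop out in each group, leaving at most 3 and at most 9.
- If no CD IIIa event was a readmission either, 6 + 2 = 8 of 9 and 6 + 5 = 11 of 15 drop out, leaving at most 1 and at most 4.

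Over these scenarios, 0 to 8 of the 9 eTEP events and 0 to 11 of the 15 open RS events might not count.

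**Step 3, contrast under nested grade cuts, used as proxies.** With a events in eTEP and b in open RS, the ratio is b/a and the difference is (b − a)/30. The Wald 95% interval is the difference ± 1.96 × √[p₁(1 − p₁)/30 + p₂(1 − p₂)/30], with p₁ = a/30 and p₂ = b/30. The p-value is from a two-sided Fisher exact test.

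| Events counted | eTEP | Open RS | Ratio | Difference (95% CI), points | Fisher p |
|---|---|---|---|---|---|
| All grades | 9 | 15 | 1.67 | 20.0 (−4.3 to 44.3) | 0.19 |
| CD II or higher | 4 | 10 | 2.50 | 20.0 (−0.8 to 40.8) | 0.13 |
| CD III | 3 | 9 | 3.00 | 20.0 (0.4 to 39.6) | 0.10 |
| CD IIIb | 1 | 4 | 4.00 | 10.0 (−3.8 to 23.8) | 0.35 |
| CD I-II alone | 6 | 6 | 1.00 | 0.0 (−20.2 to 20.2) | 1.00 |

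For example, for CD III: 9/30 − 3/30 = 0.20; the standard error is √(0.1 × 0.9/30 + 0.3 × 0.7/30) = √(0.003 + 0.007) = 0.10; 0.20 ± 0.196 gives 0.004 to 0.396.

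The intervals and p-values treat each event as a separate participant and ignore the matching. The protocol gives events, not participants with an event, so they are indicative only.

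**Step 4, reading the table.** CD I-II events are balanced at 6 against 6. Removing them leaves the difference at 6 events (15 − 9 = 9 − 3 = 6) and raises the ratio from 1.67 to 3.00. The direction is the same under every cut with an imbalance, and no Fisher test reaches 0.05.

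**The case against.** The strongest reply is that no breach of the rule is shown. A reader might infer from 12 events in the two lowest grades that outpatient events were counted. The documents do not prove it: grade and readmission are separate attributes, a low-grade event may lead to readmission, and a IIIa event may be handled without one. This stands, so non-readmission must remain an assumption.

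A reader might also infer that the group comparison hinges on the rule. On the proxies in the table only the relative measure moves materially when CD I-II events are dropped, and the equal minor-event counts give no sign of group-aware inclusion, though they cannot exclude it.

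A third tempting inference is that the 30-day limit cuts through the follow-up visit, because 1.2.20 mentions a "postoperative consultation at approximately one month after surgery". That phrase qualifies the recurrence statement only. Nothing says that complications were found or dated at that visit, and an earlier event noted there can still be placed by its onset. The visit's timing is therefore no evidence of lost events.

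Finally, the tally stands under adverse events, also covers the hospital stay and conversions, and 3.1.10 foresees reporting unintended events. This softens the gap but does not close it: 3.1.10 also ties adverse events to the secondary outcomes in 1.2.17, and the readmission outcome defined there is not reported anywhere in 1.2.20.

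**Conclusion.** The point holds as a mismatch between definition and report. The outcome in 1.2.17 cannot be derived from 1.2.20, and taken literally its rule is too narrow for the objective in 2.1.2. Whether the rule was followed is unknown.

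If no CD I-II event was a readmission and every CD III event was, the contrast is 3 against 9 instead of 9 against 15: ratio 3.0 instead of 1.67, with the same 6-event difference and direction. The true readmission contrast could lie outside these proxies, because any subset of the listed events may have been readmissions. The documents support neither a claim that the reported comparison is wrong nor one that its direction would change. This is a secondary outcome, but it carries the post-discharge safety comparison and should be settled before publication, which 1.2.20 records as still pending.

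**What to change.** Keep the 30-day window in 1.2.17, dated by event onset, and report two outcomes separately, each as participants with at least one event:

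- (a) readmission within 30 days, as 1.2.17 defines it;
- (b) any Clavien-Dindo graded complication found in the record after discharge, whether at an outpatient visit, an emergency visit or a readmission.

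Write one inclusion rule before the re-read begins, apply it to all 60 records, and state which rule produced the counts now in 1.2.20. Disclose (b) as added after the definition in 1.2.17 and with results already known. The window should not be lengthened at this stage, since that would be a further change made after seeing the results.

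The cost is a change of wording, a re-read of 60 records and a disclosed post-hoc outcome. The re-read remains unmasked; a written rule limits discretion but does not remove it.

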2.1 Introduction

2.1.1 Background and Rationale:

Extended view totally extraperitoneal prosthesis (eTEP) repair is a fairly new, up-and-coming technique as a treatment option for ventral abdominal wall hernias. The endoscopic eTEP approach has been proven to be a feasible approach [4, 5]. Our center recently started offering this treatment option from September 7, 2021 (first performance of the eTEP surgery within our center) onwards as a minimally invasive alternative to an open Rives-Stoppa [6] repair. A quick search revealed some comparisons of eTEP with IPOM [7], or comparisons between robotic and endoscopic eTEP [8], but little or no information could be found about comparisons between endoscopic (non-robot-assisted) eTEP and open Rives-Stoppa repair. Since the endoscopic eTEP repair and the open Rives-Stoppa repair both consist of a retromuscular mesh placement, and the endoscopic eTEP procedure is offered as a minimally invasive alternative to an open Rives-Stoppa repair in our center, an objective comparison between the two of them seemed logical.

2.1.2 Objectives:

To compare the outcomes of endoscopic eTEP repair versus open Rives-Stoppa repair in terms of length of hospital stay, postoperative pain management and complications.

2.1.3 Trial Design:

Partially retrospective, partially prospective, two-group, parallel, observational, superiority cohort study with an allocation ratio of 1:1.

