3.1.10 Methods: Data monitoring

A specific data monitoring committee other than the primary sponsor was deemed irrelevant given the observational nature of the study. Interim results will only be available to the primary sponsor. No specific stopping guidelines are in effect.

Adverse events are part of the secondary outcomes (1.2.17) and will be given within the final report. Unintended events will also be reported within the final manuscript.

Auditing of intended trial conduct was assessed at ethics review during the meeting of "Commissie voor Ethiek" at AZ Alma on June 8, 2022. No further auditing is intended.

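### Postoperative complications before discharge belong to no defined outcome, and the window that is defined opens at the end of a primary endpoint

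*Protocol*

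**What the plan says.** Section 1.2.17 lists two complication outcomes. The intraoperative one covers the operation only. The postoperative one is fixed by "Method of measurement: Adverse event occurrence by readmission" and "Timepoint: After discharge until 30 days postoperative".

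The two primary outcomes in Section 1.2.16 do cover the stay, but they are length of stay, measured "Start at day of operation (day zero) until day of discharge", and analgesic use. Neither records complications.

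The objective in Section 2.1.2 is to compare the two repairs "in terms of length of hospital stay, postoperative pain management and complications", with no restriction to the period after discharge. Section 3.1.10 states: "Adverse events are part of the secondary outcomes (1.2.17) and will be given within the final report". That refers back to 1.2.17 and adds no window. Section 3.1.4 likewise sends all outcomes to 1.2.16 and 1.2.17.

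The adverse-event results in Section 1.2.20 nevertheless have an in-hospital category: "During hospital stay in the eTEP group: 1x CD I, 12x CD II" and "During hospital stay in the Open RS group: 4x CD I, 10x CD II, 4x CD IIIb". The brief summary in the same section adds: "Median length of hospital stay was longer in the open RS group".

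**The concern.** There are two linked problems.

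1. **A gap in the definition.** A complication that arises on the ward before discharge is neither intraoperative nor post-discharge, so it belongs to no outcome. The objective plainly includes such events and the results section reports them. A reader cannot tell which complication comparison was planned, and an author could choose between two windows with the results in hand.
2. **A window anchored on a post-treatment event.** The window opens at discharge and closes at a fixed postoperative day 30. Discharge is affected by the treatment and by complications, and it is the end of a primary endpoint. An event on a given postoperative day can count for a patient already at home and not for one still in hospital. With the longer median stay in the open arm, this need not balance out.

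At stake is the complication comparison, above all for severe events, where the contrast between arms changes with the window.

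**Working it through.** The protocol states no figure that depends on this definition, so there is none to reproduce. The check sets the windows beside the counts in Section 1.2.20 (CD = Clavien-Dindo grade).

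| Period | Arm | I | II | IIIa | IIIb | Total | III or higher |
|---|---|---|---|---|---|---|---|
| In hospital | eTEP | 1 | 12 | 0 | 0 | 13 | 0 |
| In hospital | Open | 4 | 10 | 0 | 4 | 18 | 4 |
| After discharge to day 30 | eTEP | 5 | 1 | 2 | 1 | 9 | 3 |
| After discharge to day 30 | Open | 5 | 1 | 5 | 4 | 15 | 9 |

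**Share outside the stated window** = in-hospital events / all reported postoperative events.

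- Both arms: (13 + 18) / (13 + 18 + 9 + 15) = 31/55 = 56%.
- eTEP: 13/22 = 59%.
- Open: 18/33 = 55%.

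These are minimum figures. The outcome also requires readmission, and the protocol does not say which of the 24 post-discharge events were readmissions.

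**All-grade event ratio, eTEP to open.** In the window 9/15 = 0.60; from surgery to day 30, 22/33 = 0.67. The change is small.

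**CD III or higher.** In the window 3 versus 9; from surgery to day 30, 3 versus 9 + 4 = 13. Four of 16 such events are omitted (25%), all in the open arm. For CD IIIb alone the counts are 1 versus 4 in the window and 1 versus 8 over the full period.

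**Illustration of how far the severe contrast can move.** Assume that the 3 and 9 post-discharge events of grade III or higher came from distinct participants. Let k be the number of further open-arm participants whose in-hospital CD IIIb event adds to that count. Two-sided Fisher exact test on 3/30 versus (9 + k)/30:

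| k | Open arm | p |
|---|---|---|
| 0 | 9/30 | 0.104 |
| 1 | 10/30 | 0.057 |
| 2 | 11/30 | 0.030 |
| 3 | 12/30 | 0.015 |
| 4 | 13/30 | 0.007 |

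The test ignores the matching on gender and age in Section 1.2.12, and the post-discharge counts are not confined to known readmissions. The series shows sensitivity and is not a result.

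**Time at risk.** The window lasts 30 days minus length of stay. The protocol gives no stay in days, so these stays are assumed (eTEP versus open): 2 versus 4 days leaves 28 versus 26 (1 − 26/28 = 7% shorter in the open arm); 3 versus 6 leaves 27 versus 24 (11%); 2 versus 8 leaves 28 versus 22 (21%). This shows only the direction of the effect.

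**The case against.** The strongest reply is that nothing is hidden. Section 1.2.20 gives in-hospital complications by arm and grade, and Section 3.1.10 promises that unintended events will also appear in the manuscript. The brief summary makes no statistical comparison of complications, so no published contrast is yet affected. That stands, and it limits the weight of the point: the fault lies in the outcome definition, not in disclosure. It does not close the gap, because Section 3.1.10 ties adverse events to 1.2.17 and the objective names complications as a comparison.

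A second reply is that the data do not bear out the discharge-anchoring mechanism. If a longer stay hid more events, the open arm should lose the larger share, yet it loses slightly less (55% against 59%). This also stands for all grades. Only the four severe open-arm events point the other way, and without days of stay the difference in time at risk cannot be measured. The anchoring is a structural weakness of the definition, not a demonstrated all-grade bias.

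Third, the p-values rest on an unverified step from events to participants, use an unpaired test, and start from a count that is not strictly the defined outcome. This is correct. The raw counts, 3 versus 9 and 3 versus 13, carry the argument.

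**Conclusion.** The concern holds. As written, the postoperative complication outcome leaves out every complication between end of surgery and discharge: at least 31 of 55 reported events (56%) and 4 of 16 events of CD III or higher, all four in the open arm. The counts show a distortion between arms for severe events only.

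Confidence is high on the definitional gap and the sums, which need only Sections 1.2.17 and 1.2.20. The significance range further assumes distinct participants after discharge. The size of any effect from the discharge-dependent start cannot be determined from the protocol. The point should be fixed. It concerns a secondary outcome and can be corrected by re-tabulation and labelling; neither primary outcome changes.

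**What to change.** - Keep the outcome in Section 1.2.17 and report it exactly as defined: after discharge, by readmission.
- Beside it, report postoperative complications from end of surgery to postoperative day 30, in hospital or after discharge, with or without readmission. Tabulate per participant by highest Clavien-Dindo grade, with a category for none.
- State how many participants lie behind each event count, and which post-discharge events were readmissions.
- Declare the wider outcome in the protocol additions and in the manuscript as a post hoc change made after results were known.

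The cost is small. In-hospital events are already graded, so the work is a per-participant re-tabulation from records already reviewed. Section 1.2.20 says journal publication has not yet been achieved, and Section 4.1.2 provides for amendments to be listed at the top of the protocol. The downside is that recruitment is complete and results are posted, so the wider outcome is a results-aware departure. It can supplement the defined outcome but cannot replace it.
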